4.4.3 BRAF

Different publications have established the prognostic and predictive role of the BRAF mutation in metastatic colon cancer. The BRAF mutation is present in 5 to 8% of cases. In the OPUS study (discussed above), a retrospective analysis was made of the prognostic and predictive value of this mutation in the patients included in the study. The percentage of patients with mutated BRAF was 7.9%, and this mutation was associated with both overall survival (HR 1.82, 95% CI 1.36-2.43) but not with progression-free survival (HR 1.14, 95% CI 0.86-1.52). . There are other studies, such as

those of Di Nicolantonio et al. (JCO 2008) and Laurent-Puig et al. (JCO 2009) who also evaluate the prognostic and predictive role of BRAF. In both studies, the BRAF mutation was associated with poorer overall survival and worse progression-free survival. Own data (under review, pending publication) confirm these results. The interest of studying this marker, rather than identifying it as a new prognostic marker, lies in establishing its magnitude in the context of other prognostic markers (creation of a score), as proposed in this protocol.

4.4.4 PTEN

PTEN, like BRAF, is another component of the MAPK signaling pathway and therefore its mutational status could affect the efficacy of cetuximab. In the Laurent-Puig study discussed above (JCO 2009) they also evaluate this marker. PTEN expression was absent in 19.9% of KRAS WT patients and was associated with both progression-free survival and overall survival. Similarly, another study (Loupakis et al. JCO 2009) evaluated the predictive role of loss of PTEN expression in metastases in patients with colorectal cancer in progression to irinotecan treated with irinotecan plus cetuximab. In this study, the loss of PTEN expression in metastases was shown to be associated with worse progression-free survival ($p = 0.005$).

For all this, we consider that the expression of PTEN, together with BRAF, is another of the markers that we must include in the characterization of the MAPK pathway in this protocol.

4.5 Rationale for this trial

Advanced and / or metastatic colorectal cancer (CCRA) is a heterogeneous disease and the classification of patients is currently poor. Approximately twenty percent of patients have favorable stages (less than 4 nodules in the liver and less than 5 cm) and are suitable for local treatments (surgery or local ablative therapies). Additionally, 10-15% of patients have a poor functional status (ECOG > 2) or are impaired due to geriatric syndromes and / or co-morbidity with diseases that oppose any strategy other than the best supportive therapy. . The rest of the patients (suitable patients not suitable for radical surgery) constitute the population of patients treated with palliative therapies. Despite this, not all patients have the same prognosis. Patients with ECOG 0.1 and LDH levels <ULN (intermediate-risk patients) have better PFS and OS regardless of therapy in all randomized clinical trials (de Gramont et al, JCO 2000; Douillard et al, Lancet 2000; Koopman et al, 2007).

The CRYSTAL study shows a benefit in PFS (1.5 months) in non-mutated KRAS from FOLFIRI plus cetuximab compared to FOLFIRI alone. Currently, the selection of patients for treatment with cetuximab is based on the KRAS mutational status, which allows selecting those patients who will not respond to therapy. Other activity markers should be evaluated.

PTEN

The cytoplasmic expression of PTEN is inversely associated with PFS in colorectal cancer. There are two main retrospective studies evaluating PTEN expression in patients treated with cetuximab. Prospective validation of this marker has not yet been developed.

Clinical Hypothesis

Our hypothesis is that the proposed markers will make it possible to select those patients who will benefit the most from biweekly cetuximab treatment.

Single-arm, multicenter, prospective phase II clinical trial for biomarker validation in patients with advanced and / or metastatic colorectal cancer with non-mutated KRAS gene treated with chemotherapy plus biweekly cetuximab as first-line therapy

4.6 OBJECTIVES

4.6.1 Principal Objective

Validation of the biomarkers BRAF, IGF1P / MMp7 (DP) and PI3K-PTEN to predict PFS in patients with advanced and / or metastatic colorectal cancer with non-mutated KRAS treated with standard chemotherapy plus biweekly cetuximab as first-line therapy.

To identify new biomarkers that can predict progression-free survival (PFS) in non-mutated KRAS patients treated with biweekly chemotherapy (QT) and cetuximab in first-line therapy.

The need to identify additional biomarkers of cetuximab efficacy stems from the small predictive value of the current classification, based on KRAS mutational status, of the efficacy of biweekly cetuximab administration in the group of patients with the disease under study.

The proposed biomarkers are:

- 1 BRAF mutations
- 2.IGF-1Rp / MMP-7 (DP)
- 3.PIK3CA-PTEN.

Identifying additional factors that determine the efficacy of biweekly cetuximab will provide the scientific community with additional stratification factors for clinical trial design and better patient selection for biweekly cetuximab treatment.

4.6.2 Secondary Objectives

Secondary biological markers (MMP-7, IGF-1 and IGFBP3) will be analyzed in serum and tumor tissue to predict acquired resistance.

SG based on proposed classification

Objective response according to RECIST 1.1 (E.J. Cáncer 2009; 228-47)

Describe the safety profile of the Cetuximab 500 mg / m² every 2 weeks administration regimen in the first-line setting including the incidence of AE and significant changes in laboratory parameters.

To assess the objective response rate (ORR) and duration of response (RD) and overall survival (OS) in subjects treated with biweekly cetuximab in combination with FOLFOX6 (m) or FOLFIRI (m) as a first-line chemotherapy regimen. for subjects with metastatic colorectal cancer with non-mutated KRAS, according to the expression of the different proposed biomarkers.

5. EXPERIMENTAL PLAN

5.1 Study Design

Single-arm, multicenter, and prospective phase II clinical trial for validation of biomarkers in patients with advanced and / or metastatic colorectal cancer with non-mutated KRAS gene treated with chemotherapy plus biweekly cetuximab as first-line therapy. Patients with non-mutated CCRAyM and KRAS will be eligible.

Patients will be recruited over a 24-month period.

Before inclusion in the study and to confirm eligibility, the investigator or designee will send a sample of the primary tumor to the CUN, which will centrally review the status of KRAS (if the patient already has a prior determination of the status of the KRAS gene, it can be included in the assay without the need to re-determine K-RAS). At the same time, the investigator or designee will review existing radiological images in addition to any other relevant clinical documents (reports, notes, etc.) to confirm that the subject has previously untreated advanced and / or metastatic colorectal cancer.

The proposed biomarkers will be measured at the beginning of the study. Investigators can treat patients with CCRAyM and non-mutated KRAS with biweekly FOLFOX6 (m) or FOLFIRI (m) + cetuximab. Other investigative agents will be excluded.

FOLFIRI (m) / FOLFOX6 (m) will be administered once every 2 weeks until 6 months of treatment, disease progression (PE), or unacceptable toxicity. Cetuximab will be administered every 2 weeks as stipulated in this protocol until disease progression. If patients do not show progression after 6 months of treatment with FOLFIRI (m) and FOLFOX6 (m), they will continue to receive biweekly cetuximab as monotherapy until progression.

Subjects who stop receiving FOLFOX6 (m) / FOLFIRI (m), for example due to toxicity, may receive biweekly cetuximab as monotherapy until disease progression. Following discontinuation of biweekly cetuximab, the treatment period will end and subjects will attend a follow-up safety visit 30 ± 3 days later.

Throughout the trial, subjects will be assessed for tumor response using Response Assessment Criteria for Solid Tumors (RECIST 1.1). The tumor response of the subjects will be evaluated by CT (helical or conventional) thoracic and abdominal performed in the baseline phase and every 12 weeks (three months) until the progression of the disease. In subjects with symptoms that indicate disease progression, tumor response should be assessed at the time of symptoms.

Serum biomarker measurements will be performed: until disease progression is documented (every 12 weeks +/- 1 week).

All subjects who discontinue treatment before disease progression (eg, due to unacceptable toxicities) will be followed for PFS (eg, radiographic tumor evaluations) every 12 weeks until progression of the disease or the end of the study (unless the reason for abandoning the study is the total withdrawal of consent).

Once the patient has progressed, the long-term follow-up period of 24 months will begin from the date of progression (every 3 months).

Single-arm, multicenter, prospective phase II clinical trial for biomarker validation in patients with advanced and / or metastatic colorectal cancer with non-mutated KRAS gene treated with chemotherapy plus biweekly cetuximab as first-line therapy

K-RAS, in patients who do not have a previous determination, and other markers of tumor tissue will be measured at the University Clinic of Navarra (CUN) and the markers of the blood samples will be measured at the Hospital Clínic de Barcelona (HCB) .

Biomarkers will be measured prior to patient enrollment. In addition, blood samples will be collected every 3 months until disease progression.

The proposed biomarkers (BRAF, MMP7 / IGF-1RP / MMP-7 (DP), PIK3CA-PTEN) will be used as independent variables in a multivariate model containing other established prognostic variables to predict PFS. A classification will be constructed based on the ability to predict the response of the biomarkers.

5.1.1 Premature withdrawal of treatment:

Treatment will be interrupted in case of:

Withdrawal of consent from the patient

[figure not shown]
Progressive disease

Intolerable toxicity

Investigator's decision based on what he considers best for the patient

Single-arm, multicenter, prospective phase II clinical trial for biomarker validation in patients with advanced and / or metastatic colorectal cancer with non-mutated KRAS gene treated with chemotherapy plus biweekly cetuximab as first-line therapy

Study Schema

a Day 1 = day of the first treatment administration.

b Subjects' tumor response will be assessed every 12 weeks, throughout the trial until PE (per revised RECIST 1.1 criteria) or withdrawal from the study.

c Subsequent cycles could be delayed due to toxicities associated with cetuximab or chemotherapy.

d All subjects who permanently discontinue treatment (discontinuation is considered completion of all treatment) for any reason will undergo a follow-up safety assessment 30 days \pm 3 days after the last dose of treatment. After the safety follow-up visit, subjects who have not progressed will be followed up every 12 weeks as defined in the study. Subjects who undergo surgery for metastases should follow the controls every 12 weeks as established in the protocol. In case of progression by RECIST 1.1 criteria ., Subjects will be monitored for disease status, subsequent cancer treatment, and survival (long-term follow-up).

e All subjects who discontinue treatment prior to disease progression (eg, due to unacceptable toxicities) will be followed up for PFS (eg, radiographic tumor assessments) every 12 weeks until the progression of the disease or the end of the study (unless the reason for abandoning the study was the total withdrawal of consent).

f The end of treatment is understood to be the last day the patient has received the last drug of the combination under test (FOLFOX6 (m) / FOLFIRI (m) / Cetuximab). The safety visit should be carried out 30 \pm 3 days after the end of the treatment, regardless of the cause that caused it. If the patient has not progressed, imaging and biomarker determinations should continue every 12 weeks until progression as specified in this protocol.

g. In order to mobilize any biological sample, the signing of the informed consent will be mandatory. If the patient already has a previous determination of the status of the KRAS gene, he can be included in the test without it being necessary to re-determine the mutational status of K-RAS.

5.2 Number of sites

Approximately 30 centers in Spain will participate (see attached list)

5.3 Number of subjects

The participants in this clinical investigation will be called subjects.

The expected sample size is 170 subjects enrolled to receive chemotherapy. The justification for the sample size can be found in section 10.2.5.

5.4 Estimated study duration

5.4.1 Study duration for the participants

The inclusion period is expected to last approximately 24 months.

Throughout the trial, subjects will be assessed for tumor response using Response Assessment Criteria for Solid Tumors (RECIST 1.1). The tumor response of the subjects will be evaluated by CT (helical or conventional) thoracic and abdominal performed in the baseline phase and every 12 weeks (three months) until the progression of the disease. In subjects with symptoms that indicate disease progression, tumor response should be assessed at the time of symptoms.

To assess overall survival, all patients will be followed up by visits to the center or by telephone contact every 12 weeks \pm 4 weeks from the date of progression up to 24 months after inclusion or death of the last subject, which happen first.

Therefore, the estimated maximum duration of the study is about 48 months (4 years).

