8.6 Long-term follow-up visits

After disease progression, all subjects will be contacted through a clinic visit or by phone (by a member of the center's staff) to assess disease status, subsequent anticancer therapy, and survival after the last drug administration. in study. They will be contacted every 12 weeks \pm 4 weeks from the visit (follow-up or security) until 24 months after the last inclusion or death of the last subject, whichever occurs first.

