- h. If thoracic CT scan at selection did not show any chest abnormality, chest X-ray imaging were performed in subsequent evaluations. A CT scan was performed to confirm any abnormality identified upon chest X-ray imaging performed after selection, and all subsequent evaluations were thoracic CT imaging.
- i. Response evaluation was conducted according to the revised RECIST 1.1 criteria, every 12±1 weeks until PD. Subject follow-up was performed regardless of discontinuation or a delay in treatment.
- j. ECOG PS evaluation (on day 1 of each treatment cycle).
- k. Tumour evaluation and serum CEA test was performed every 12 weeks and at the follow-up visit only in subjects who have withdrawn from the trial for reasons different from PD, and in those who have not had a serum CEA test in the previous 12 weeks.
- l. Paraffin embedded tumour block was sent to the central laboratory (Fundación Jiménez Díaz) at selection. The centralised evaluation laboratory perform a tumour block quality assessment. It was compulsory that KRAS and NRAS mutational status (wtKRAS and NRAS) was confirmed by a validated laboratory before the inclusion of any subject.
- m. Follow-up of all subjects who permanently discontinued the treatment before disease progression (e.g. due to unacceptable toxicities) was conducted to evaluate PFS (i.e., tumour imaging) every 12± 1 week until PD or until the end of study (unless the reason for study discontinuation was total consent withdrawal). After PD, all subjects underwent a follow-up assessment of disease status, subsequent cancer therapy, and survival assessment every 12 ± 1 weeks until the end of study (maximum of 24 months).
- n. Blood samples for biomarker analysis were withdrawn before the study treatment initiation and every 12 weeks ± 1 weeks until PD.

Table 3: SDV schedule

Form	Variables
Eligibility	Pathology report, staging, prior treatment.
Demographics	Date of birth, ECOG PS, ICF (signature, date, and completion)
Primary tumour	Diagnosis date, location, staging and surgery
Adjuvant or neoadjuvant treatment	Yes/No
KRAS/NRAS	Central reviewing
Baseline biochemistry and SAE biochemistry	LDH, creatinine, bilirubin, and CEA
Baseline haematology and SAE haematology	Haemoglobin, platelets, and leukocytes

Metastasis	Nº affected organs and hepatic M1 (number and size)
CT scans or MRI	All variables (date, lesions measure, location, new lesions) and RECIST criteria
AEs	Grade and need of SAE communication

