7. RESULTS

Table 4 Disposition of patients

Patients enrolled	
Received at least one cycle of study treatment	
Evaluable patients	
End of study (evaluable population)	
Death	
Lost to follow-up	
Censored at database closure	
Study completion (24 months of follow-up after PD)	

Table 5 Protocol deviations

Deviation type	Total
Informed consent form	
Efficacy criteria	
Eligibility criteria	
Incorrect dosing regimen	
Other	
Safety	

Table 6. Baseline characteristics by biomarker

	wtBRAF (n=161)	Mutant BRAF (n=20)	p-value*	wtPI3K and PTEN >3 (n=69)	Mutant PI3K or PTEN ≤3 (n=98)	p value*	Non-DP (n=158)	DP (n=23)	p value*
Female									
Mean age (SD)									
Primary location									
Ascending colon									
Transverse colon									
Descending colon									
Sigmoid colon									
Rectum									
Stage									
I									
II									
III									
IV									
Surgery of the primary tumour									
Performance status									
0									
1									
2									
Number of metastatic organs									
0									
1									
2									
3									
4+									
Liver metastasis									
0									
≤3, ≤5 cm									
>3 or >5 cm									
Node metastases¹									
Lung metastases¹									
Peritoneal metastases¹									

Patients with only resectable liver metastases ²									
Chemotherapy									
FOLFOX+Cetuximab									
FOLFIRI+Cetuximab									
Mean Leucocytes (SD)									
Mean Haemoglobin (SD)									
Mean Platelets (SD)									
Mean ALP (SD)									
LDH >450									
Mean CEA (SD)									

¹

- Fisher's exact test for categorical variables and Wilcoxon rank-sum test for ordinal or continuous data

² Missing in one patient The patient does not have metastasis in any other location, and those in the liver are ≤ 3 in number and ≤ 5 cm in size.

Table 7. MEASUREMENTS OF TREATMENT COMPLIANCE

	Total (n=)
Treatment disposition	
Received at least one injection (safety population)	
Efficacy population	
Received at least 12 cycles of cetuximab	
Received at least 12 cycles of chemotherapy+cetuximab	
Received less than 12 cycles of cetuximab	
Received 3 or less administrations of combination	
FOLFOX+cetuximab	
FOLFIRI+cetuximab	
End of Treatment (EOT)	
Reasons for end of treatment	
PD	
PI decision (24 due to surgery, 2 radiotherapy, 2 complete response, 49 others)	

Patient decision	
Toxicity (related to treatment)	
AE (unrelated to treatment)	
No data of EOT available	

Table 8: Patients excluded from the efficacy or safety analysis

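### Survival follow-up has two incompatible stops, and the progression-based one contradicts the 48-month duration and ties OS censoring to PFS

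*Protocol*

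**What the plan says.** The stop of survival follow-up is worded differently in five places:

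- **Protocol 5.1 (Study Design)** runs a clock for each patient: "Once the patient has progressed, the long-term follow-up period of 24 months will begin from the date of progression".
- **Protocol 8.6 (Long-term follow-up visits)** sets a common date for all subjects: "until 24 months after the last inclusion or death of the last subject, whichever occurs first".
- **Protocol 5.4.1 (Study duration for the participants)** has contacts run "from the date of progression up to 24 months after inclusion or death of the last subject", again whichever comes first, and concludes from this that the study lasts at most about 48 months.
- **SAP section 6, Table 2, footnote m** has assessments after progression run "until the end of study (maximum of 24 months").
- **SAP section 7, Table 4** has the disposition category "Study completion (24 months of follow-up after PD").

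Protocol 5.4.2 ends the study when the last subject completes the long-term follow-up period or dies, so its meaning depends on which rule defines that period. OS is censored at last contact (Protocol 10.2.2; SAP 6.5.1.2). Neither document says how to treat a patient whose contacts ended by design 24 months after progression.

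**The concern.** The progression clock and the calendar stop produce different OS data. Under the calendar stop, the potential follow-up of a patient depends only on the enrolment date. Under the progression clock it equals that patient's PFS plus 24 months. Early progressors then leave the risk set sooner than late progressors. If early progression goes with earlier death, the late part of the Kaplan-Meier curve rests too heavily on patients with a better outlook.

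OS by the proposed classification is a secondary objective, and that classification is built to separate PFS. The compared groups would therefore differ in potential OS follow-up by construction. About 30 centres (Protocol 5.2) could also follow different pages, so OS maturity could vary by site.

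**Working it through.** **1. The stated duration.** Protocol 5.4.1: "The inclusion period is expected to last approximately 24 months". Adding 24 months of follow-up after the last inclusion gives 24 + 24 = 48 months, the stated figure. First inclusion in the fourth quarter of 2010 plus 48 months is the fourth quarter of 2014, which matches the end date in Protocol 3.9. A stop at each patient's own inclusion + 24 months would also give 48.

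**2. The progression clock.** The last-enrolled patient finishes at 24 + time to progression + 24 months.

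| Time to progression (months) | Source of the value | Last patient ends (months) |
|---|---|---|
| 8.3 | median PFS, cited phase II cetuximab arm | 56.3 |
| 9.9 | median PFS, cited phase III cetuximab arm | 57.9 |
| 12 | horizon of the sample-size assumption | 60 |

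There is no fixed maximum, and each of these ends falls in 2015.

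**3. The calendar in the SAP.** SAP 6.5.2 gives 47 months of recruitment and 70 months in total, leaving 70 − 47 = 23 months after the last recruitment. A patient enrolled last cannot complete progression + 24 months. Conversely, a patient enrolled at the start who progresses at 6 months would stop at month 6 + 24 = 30, which is 40 months before closure.

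**4. Effect on the OS curve.** Inputs from Protocol 4.1 are the medians in the cited phase III cetuximab arm: PFS 9.9 and OS 23.5 months. Assumptions not in the documents are exponential PFS and post-progression survival, linked by a shared gamma frailty with variance 0 to 1. One million patients were simulated per row, with OS censored at PFS + 24. Differences are taken before rounding.

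| Frailty variance | Alive 24 months after progression | OS at 36 months: true / Kaplan-Meier (difference) | OS at 42 months: true / Kaplan-Meier (difference) |
|---|---|---|---|
| 0 | 17.4% | 27.3% / 28.5% (1.1) | 19.9% / 21.7% (1.8) |
| 0.25 | 21.2% | 31.6% / 32.8% (1.2) | 25.6% / 27.6% (2.0) |
| 0.5 | 24.1% | 34.5% / 35.7% (1.2) | 29.4% / 31.5% (2.1) |
| 1 | 28.5% | 38.0% / 39.1% (1.1) | 34.0% / 36.0% (2.0) |

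At 24 months there is no difference, because nobody can be censored before PFS + 24. The estimated median stays at 23.5 months. Under a common stop at last inclusion + 24 (uniform 24-month accrual), the difference is zero to within 0.03 points at every time checked.

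**5. Deaths observed.** Same model, 181 patients (the SAP efficacy set), uniform accrual; each range runs over frailty variance 1 to 0.

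| Accrual | Rule | Deaths |
|---|---|---|
| 24 months (planned) | progression + 24, no other bound | 129 to 150 |
| 24 months (planned) | last inclusion + 24 | 111 to 129 |
| 47 months, closure at 70 | progression + 24, bounded by closure | 113 to 132 |
| 47 months, closure at 70 | all patients to closure | 121 to 146 |

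The first two rows combine the final efficacy set with the planned accrual, so they are illustrative. On the actual calendar the common cut-off gains about 8 to 14 deaths.

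**The case against.** The strongest reply is that this is a small wording inconsistency, partly handled already. SAP 6.5.1.5 censors patients still in the study at database closure at the date last known alive, and SAP Table 4 has a row for that. The 23 months between last recruitment and the end are close to the Protocol 8.6 rule. That stands in part: a calendar closure did bound follow-up. It does not remove the separate category for patients who completed at progression + 24.

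Several stronger readings are tempting but not supported.

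- **Three different stops.** In the 5.4.1 sentence the last subject can govern both inclusion and death. The sentence parallels 8.6 and leads straight to the 48 months. Two rules are certain; a third exists only on the literal per-patient reading. That reading would stop follow-up near the cited median OS of 23.5 months, so the sentence needs rewording either way.
- **Only the 8.6 rule fits 48 months.** Each patient's own inclusion + 24 fits too. Only the progression clock fails.
- **The progression rule costs about 25 deaths.** With exponential OS (median 23.5 months), 181 patients give about 92 deaths at own inclusion + 24 (181 × 50.7%) and about 117 at last inclusion + 24 with 24-month accrual (181 × 64.7%). That contrast concerns the doubtful reading of 5.4.1, not the progression clock. On the planned accrual an unbounded progression clock yields more deaths than the calendar stop.
- **The comparison between marker groups is badly distorted.** A simulation with a PFS hazard ratio of 1.79 (SAP 6.5.2) and post-progression hazard ratios of 1.0 to 1.79 moved the OS hazard ratio by at most about 0.07 between the two rules. With frailty, the progression clock was the closer of the two to the complete-follow-up value. A material bias in the hazard ratio is not shown.

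**Conclusion.** The concern holds as a contradiction between two stop rules in current text, with a real but small consequence for a secondary endpoint. The progression-based stop conflicts with Protocol 8.6, with the stated 48 months and with the 2014 end date, and Protocol 5.4.2 inherits the conflict. That part rests on the documents and simple arithmetic.

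That this stop makes OS censoring a function of PFS follows from its definition. The size of the effect, about 1.2 points at 36 months and 1.8 to 2.1 at 42, rests on the assumed medians, exponential form and frailty range. It is confined to the curve beyond 24 months. A change is worth making because a change of wording removes the bias.

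**What to change.** Adopt one common calendar cut-off for all patients, 24 months after the last inclusion as in Protocol 8.6, which agrees with the 48 months.

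- Carry it into Protocol 5.1, 5.4.1 and 5.4.2 and SAP Table 2, footnote m. In 5.4.1, say last inclusion.
- Replace the progression + 24 completion category in SAP Table 4.
- State that OS is censored at the last contact on or before the cut-off.
- If follow-up is already complete, state which rule was applied and report OS with a common cut-off where the data allow.

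The cost is wording plus more 12-weekly contacts, by visit or telephone, for early progressors. Late-enrolled patients would stop sooner than under progression + 24, so on the planned 24-month accrual fewer deaths would be observed (111 to 129 against 129 to 150 in the illustration). On the actual 47/70-month calendar the common cut-off gains deaths. The trade-off should be stated when the rule is chosen.
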